Additionally, a group of 10 individuals with stroke will have an MRI on two visits. In order to be considered for this SUBSTUDY, participants will first be enrolled in the above study. The purpose of this SUBSTUDY is to gather preliminary data on patterns of neural activity that are associated with better performance outcomes in the rehabilitation intervention. We also seek to determine if the intervention is able to change baseline functional brain connectivity. This is a critical piece of knowledge to have in order to accurately understand and interpret the primary goals of the Main study. With this knowledge we can more effectively analyze and interpret the data gathered from the main study. This SUBSTUDY is non-significant risk.

Anatomical image acquisition. High-resolution structural scans will be obtained using an inversion recovery 3D spoiled gradient echo (3DSPGR) sequence using a matrix size of 256 x 256, field of view of 24 cm, section thickness of 1.5 mm with no gap between sections, and 128 slices, giving an in-plane resolution of 0.94 mm. This sequence will be used for anatomic overlays of the functional data and for spatial normalization to a standard atlas.

Functional MRI task and acquisition. Each participant will be asked to watch a movie of hand movements on a monitor and mimic the ongoing actions with their own hands. Participants will be asked to do two, 6 min runs of the task. Each functional run consists of movement blocks interspersed with rest blocks. Following each rest block there will be a preparation block in which the participant will receive a preparation cue which counts down the number of seconds remaining before the motor task begins again. This preparation block will be modeled separately in the statistical analysis and used to eliminate the effects of attentional set-shifting to the visuo-motor performance data acquired in the task block. All participants performed a practice session before the functional MRI scan in order to limit the contribution of learning to the data acquired.

Experiments will be conducted on a 3T MR scanner with twin-speed gradients and a birdcage head coil (3T

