Siemens Trio). Whole-brain activation will be assessed by examining the blood-oxygenation-level-dependent (BOLD) signal by measuring changes in the T2*-relaxation rate that accompany changes in blood oxygenation associated with cortical activation. The images will be collected parallel to the anterior commissure-posterior commissure (AC-PC) line with one slice overlying the AC-PC line. Functional imaging will be performed using multislice gradient-echo echo planar imaging (TR=2500, TE=40 msec) with a field of view of 24 cm (frequency) x15 cm (phase), and an acquisition matrix of 64x40 (28 slices, 5 mm thickness, no skip). This sequence delivers an effective voxel resolution of 3.75 x 3.75 x 5 mm.

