Functional image analysis. Statistical parametric maps (SPMs) will be generated using SPM12 from the Wellcome Department of Cognitive Neurology, London, UK implemented in Matlab (The Mathworks Inc. Natick, MA, USA). Prior to generating SPMs, data will be preprocessed based on standard techniques. The raw data will be reconstructed and corrected for image distortion and alternate k-space line errors will be performed on each image on the basis of data acquired during phase-encoded reference imaging. The functional data sets will be motion corrected (intra-run realignment) within SPM12 using the first image as the reference. The functional data sets will be normalized to Montreal Neurological Institute (MNI) space and smoothed using an 8 x 8 x 10 mm Full Width at Half Maximum Gaussian smoothing kernel. The data will be modeled with a boxcar design including an explicit baseline model convolved with the hemodynamic response function. All data will be globally normalized with proportional scaling of the image means. Temporal smoothing and de-trending will be performed as part of the SPM analysis. SPMs will be generated using the general linear model within SPM12 for each subject. Group analyses will be performed using a random effects model. The random effects analysis will use the 'contrast image' generated for each subject by applying the appropriate weights to the multiple regression. The random effects analyses will utilize two sample t-tests available in SPM12 to compare activation patterns between groups. To make comparisons within groups to identify the effect of conditions, paired t-tests will be used. Secondary analyses will be performed on the fMRI data using a multiple regression technique. A variable, such as age, can be entered into the regression analysis to control for unanticipated population differences. Anatomic regions of interest will be defined automatically using an atlas-based program WFU_Pick Atlas, which runs in Matlab. All data will be thresholded at $p<0.05$ corrected for multiple comparisons using the false discovery rate.E.

PROTECTION OF HUMAN SUBJECTS

a. Human Subjects Involvement and Characteristics

Human Subjects Involvement and Characteristics: 130 individuals with post-stroke UE hemiparesis will participate in this rehabilitation research study.

Participants with stroke will be recruited from three sources:

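### Dividing each fMRI image by its own mean biases the substudy's task contrasts if the global mean follows the task, and the plan has no check for this

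*Protocol*

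**What the plan says.** The point sits in Protocol section D, under Methods specific to the SUBSTUDY. Ten enrolled patients are scanned at two visits, to gather preliminary data on "patterns of neural activity that are associated with better performance outcomes in the rehabilitation intervention". A second aim is to see whether the intervention changes baseline functional connectivity.

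Participants are to "watch a movie of hand movements on a monitor and mimic the ongoing actions with their own hands". The design is a block design: "Each functional run consists of movement blocks interspersed with rest blocks". A countdown preparation block follows each rest block and is modelled separately. On the outcome: "Whole-brain activation will be assessed by examining the blood-oxygenation-level-dependent (BOLD) signal".

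The Functional image analysis paragraph fits a boxcar general linear model in SPM12 with an explicit baseline. It then states: "All data will be globally normalized with proportional scaling of the image means". The next sentence adds: "Temporal smoothing and de-trending will be performed as part of the SPM analysis". Subject contrast images go into a random-effects analysis, with two-sample t-tests between groups and paired t-tests within groups, thresholded at 0.05 with false discovery rate control.

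Neither document says that the global signal will be tested against the task, or that an analysis without this scaling will be run. The SAP does not cover the MRI data.

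**The concern.** Image-by-image proportional scaling is harmless to a task contrast only if the global mean does not move with the task. A block task that engages visual and motor cortex against rest is a setting where it plausibly could move. The divisor would then carry part of the task effect, and dividing by it would take that amount off every voxel, including voxels that did nothing.

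Two results are exposed. Thresholded maps could lose true activation or show deactivation that is not there (or the reverse, if the mean falls). Comparisons between the two visits or between groups would also contain any difference in how far the global mean moved. Therapy might change the extent of activation, so that difference could be mistaken for a local effect of therapy.

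**Working it through.** The documents give no sample size, power or error figure for the MRI analysis, so there is no planned figure to reproduce. The check is algebra, followed by a small simulation.

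**Inputs from the Protocol.** Block design, image-mean scaling, two runs of 6 minutes, TR 2500 (read as ms), so 360 / 2.5 = 144 scans per run; 10 patients, two visits.

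**Assumed, not in the documents.** Share of in-mask voxels activated, f; their effect, e (1%); share deactivated, d; their fall, c.

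**Step 1: the shift.** The global mean changes by g = f x e - d x c. After division by the image mean, a voxel with true effect b shows (1 + b) / (1 + g) - 1, which is about b - g. An unchanged voxel shows 1 / (1 + g) - 1, about -g.

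**Step 2: no deactivation, e = 1%.** Example at f = 30%: g = 0.30 x 1% = 0.30%. An active voxel shows 1.01 / 1.003 - 1 = 0.698%; an unchanged voxel shows 1 / 1.003 - 1 = -0.299%.

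| f | g | active voxel shows | unchanged voxel shows |
|---|---|---|---|
| 2% | 0.02% | 0.98% | -0.02% |
| 5% | 0.05% | 0.95% | -0.05% |
| 10% | 0.10% | 0.90% | -0.10% |
| 20% | 0.20% | 0.80% | -0.20% |
| 30% | 0.30% | 0.70% | -0.30% |
| 40% | 0.40% | 0.60% | -0.40% |

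Proportional shrinkage is about f and hardly depends on e.

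**Step 3: with deactivation** (f = 10%, e = 1%, c = 0.5%).
- d = 10%: g = 0.10 - 0.05 = +0.05%; active 0.95%, unchanged -0.05%.
- d = 20%: g = 0.10 - 0.10 = 0; no bias.
- d = 30%: g = 0.10 - 0.15 = -0.05%; active 1.05%, unchanged +0.05%.

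**Step 4: between visits.** With local activation held at 1%, the spurious change is g at the first visit minus g at the second. If f falls from 20% to 10%, that is 0.20% - 0.10% = +0.10% in every voxel. From 10% to 5% it is +0.05%, and from 30% to 15% about +0.15%.

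**Step 5: within one scan.** Active minus unchanged at f = 30% is 0.698% - (-0.299%) = 0.997%, close to the true 1%. The shift is nearly the same everywhere, so differences between regions survive.

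**Step 6: simulation.** Two runs of 144 scans, 4000 voxels, a block-design linear model, first-level false discovery rate 0.05. Assumed: e = 1%, voxel noise SD 1.5%, global noise SD 0.3%, 20 s rest and 25 s task blocks, no preparation block, no spatial correlation. Without image-by-image scaling, the mean estimate was 0.99% to 1.01% in active voxels and -0.01% to +0.01% in unchanged ones. With scaling, the estimates matched the table in Step 2. Share of unchanged voxels falsely declared deactivated:

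| f | unscaled | scaled |
|---|---|---|
| 5% | 0.1% | 0.4% |
| 10% | 0.4% | 1.5% |
| 20% | 0.4% | 9.8% |
| 30% | 0.7% | 30.8% |
| 40% | 1.1% | 58.3% |

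These shares illustrate a single-subject analysis under assumed noise. They are not predictions for the 10-person group analysis.

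**The case against.** A reader might infer that the task does raise the global mean, so that the planned analysis will understate activation and manufacture deactivation. The documents do not support that. They describe the task but give no active share, effect size or net global change, and Step 3 shows that modest deactivation elsewhere brings the bias to zero or reverses it. This objection stands, and it is why the point is conditional.

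Size is also a fair objection. For focal activation (f of 2-5%) shrinkage is only 2-5%, and the simulated false-deactivation share at f = 5% (0.4%) lies within the 0.1% to 1.1% seen without scaling. A 0.10% shift between visits, common to all 10 patients, would reach an uncorrected two-sided p below 0.05 in a paired t-test (critical t = 2.26, 9 df) only if the SD of the paired differences were below 0.10 x sqrt(10) / 2.26 = 0.14%. Shifts in opposite directions across patients would partly cancel. Regional differences within a scan are roughly preserved (Step 5), which matters for a substudy about patterns.

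On the contrasts, a reader might take the paired t-tests to be explicitly pre-post. The Protocol assigns them to effects of conditions, and its stated change question concerns connectivity, which this check does not address. What stands is narrower: any comparison between visits or groups that uses these contrast images inherits the difference in g.

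The other safeguards do not remove the shift. De-trending acts on slow drift, not on a mean that follows the blocks. The baseline model and the random-effects step work on images already scaled. The separate preparation regressor only changes which conditions g compares. If a single factor per run was intended, the sentence does not say so. Finally, image scaling does absorb scan-to-scan global fluctuation, which de-trending does not; that is a real cost of dropping it.

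**Conclusion.** The point holds conditionally. If the global mean differs between the contrasted conditions by g, the planned scaling shifts every voxel's task effect by about -g, and nothing in the plan detects or removes this. With e = 1% and no deactivation, the understatement runs from about 2% of the true effect at f = 2% to about 40% at f = 40%. With deactivation it may vanish or change sign. All values of f, e, d and c are assumptions, and so is the reading that each image is divided by its own mean, although that is the natural one.

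The consequence is limited to thresholded maps and absolute activation in a 10-person preliminary substudy. The Aim 1 FMA-UE analysis is unaffected. This is a low-priority correction, worth making because it is cheap.

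**What to change.** Replace the global normalisation sentence in Functional image analysis with wording to this effect:

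- The main analysis uses no image-by-image global normalisation. Each run is scaled by one grand-mean factor, together with the planned de-trending.
- For each run, the correlation of the global signal with the task regressor is tested and reported by visit.
- The proportionally scaled analysis is reported only as a sensitivity analysis.

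The cost is one processing setting, one extra regression per run and a second pass of the model, with no new scans or participants. The downside is that scan-to-scan global fluctuations other than slow drift stay in the residual noise of the main analysis, which may lose some sensitivity. The scaled sensitivity analysis shows whether that matters.

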The FMA-UE item difficulty hierarchy provides a framework to elucidate and interpret contemporary research. Our results suggest that the FMA-UE items are arranged according to the difficulty of motion. That is, arm movements are “easier” or “more challenging” based on the inherent task-specific demands of the movement. Elbow flexion may be “easier” than wrist circumduction because the movement is inherently less complex, i.e., requires less agonist-antagonist coordination. Shoulder flexion to 180 degrees with the elbow extended may be “difficult” because of the influence of gravity on a long lever arm.

3b. Use of the framework to match person-ability to item-difficulty

In a separate study we aimed to illustrate the connection between a Rasch FMA-UE person-ability measure and FMA-UE item-difficulties. The data shown here were generated from [name] funded VA RR&D CDA-2 project. For this project, 55 participants (52 completed testing), ages 45–88 years who were an average of 7 years post first time ischemic stroke were enrolled into a prospective cross-sectional study of UE reaching ability.

Table 2: The Rasch FMA-UE Item Difficulty

FMA-UE item	Measure	Error
Wrist circumduction	1.67	0.10
Hook grasp	1.33	0.10
Shoulder flexion to 180°, elbow extended	1.26	0.10
Spherical grasp	1.20	0.10
Lateral prehension	1.08	0.10
Wrist flexion-extension, elbow extended	1.06	0.10
Pronation-supination, elbow extended	1.00	0.10
Wrist stable, elbow extended	0.95	0.10
Movement with normal speed	0.89	0.10
Forearm supination	0.65	0.10
Shoulder abduction to 90°, elbow extended	0.28	0.10
Movement without dysmetria	0.27	0.10
Shoulder external rotation	0.24	0.10
Wrist stable, elbow at 90°	0.18	0.10
Wrist flexion-extension, elbow at 90°	0.12	0.10
Palmar prehension	0.06	0.10
Scapular retraction	0.03	0.10
Pronation-supination, elbow at 90°	-0.17	0.11
Shoulder flexion to 90°, elbow extended	-0.21	0.11
Hand to lumbar spine	-0.40	0.11
Shoulder abduction	-0.56	0.11
Elbow extension	-0.64	0.11
Forearm pronation	-0.87	0.11
Movement without tremor	-0.91	0.11
Cylindrical grasp	-1.10	0.12
Finger mass extension (relax flexion)	-1.25	0.12
Scapular elevation	-1.40	0.12
Finger mass flexion	-1.44	0.12
Shoulder adduction with internal rotation	-1.56	0.12
Elbow flexion	-1.76	0.13

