Inclusion criteria: 1) experienced ischemic stroke at least 3 mo. prior. The lesion type and location will be confirmed with medical records and past MRI or CT scan. This criteria is based on evidence suggesting lesions located in brainstem or cerebellum⁶⁴ and hemorrhagic⁶⁵ stroke may affect neural reorganization and observable patterns of UE motor recovery differently than lesion in the MCA distribution or ischemic etiology; 2) passive range of motion in affected shoulder, elbow and wrist within functional limits; 3) 20-90 years of age. Exclusion criteria: 1) pain in the affected UE that would interfere with movement; 2) unable to understand 3-step directions; 3) orthopedic condition or impaired corrected vision that would alter kinematics of reaching; 4) Any implanted ferromagnetic object that could be displaced by a magnetic field.⁶⁶; 5) a history of seizures. The study sample shall be inclusive of the general population of adults with stroke-related UE motor impairment without restriction in regard to gender, race, age, and socioeconomic status. Every effort will be made to include women, minorities and indigenous populations.

Procedure: Informed consent and all other procedures will occur in accordance with approval from the MUSC IRB and VAMC RR&D committee.

Study Flow: **Figure 9** illustrates the study flow.

[figure not shown]

Figure 9: Study Flow

evaluator. The 3 reflex items will not be administered because our previous work showed that these items do not contribute to measurement of the construct “voluntary” UE motor function. FMA-UE item ratings will be converted to a person-measure using Rasch analysis (Winsteps⁶⁸) with item-difficulty calibrations anchored to published values⁴⁴ which will assure stable person-measure estimates.

Procedure for Neuromechanical Evaluation: Kinematic and EMG analyses will be conducted at three time points (pre, mid and post).

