If the subject agrees, the data collected and generated from this study will be shared and linked to RESTORE by the subject's registry ID. Sharing data from this study with the registry will allow for more targeted recruitment efforts in the future and allow researchers at MUSC to have a more complete registry with key stroke recovery elements including common data and physical function characteristics that are applicable to multiple studies.

Targeted/Planned Enrollment Table

Total Planned Enrollment - 130

TARGETED/PLANNED ENROLLMENT: Number of Subjects			
Ethnic Category	Sex/Gender		
	Females	Males	Total
Hispanic or Latino	3	4	7
Not Hispanic or Latino	48	75	123
Ethnic Category: Total of All Subjects*	130		
Racial Categories			
American Indian/Alaska Native	0	0	0
Asian	1	0	1
Native Hawaiian or Other Pacific Islander	0	0	0
Black or African American	16	25	41
White	34	54	88
Racial Categories: Total of All Subjects*	51	79	130

*The "Ethnic Category: Total of All Subjects" must be equal to the "Racial Categories: Total of All Subjects".

Inclusion criteria for the proposed study:

1. Experienced a stroke at least 3 months prior that has resulted in unilateral hemiparesis.
2. Passive range of motion in affected shoulder, elbow and wrist within functional limits;
3. 20-80 years of age.

Exclusion criteria for the proposed study:

1. Pain in the affected upper extremity that would limit participation in the study intervention.
2. Unable to understand 3-step directions;
3. Unable to attend the study-related treatment or evaluation sessions
4. Orthopedic condition in back or UE or impaired corrected vision that would alter kinematics of reaching.

We expect that our sample will have demographic characteristics similar to that of the general population in this region of South Carolina. These percentages, based on the 2010 census, reveal that the Charleston county area has a population that is 64% white, 30% African-American, 1% Asian, and 5% Hispanic and Latino and 39% female. There will be a total of 130 individuals with post-stroke UE hemiparesis enrolled in the overall study, and 10 subjects enrolled in this substudy..

No children will be included in this study.

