The following information will be obtained from human subjects: Name, age, contact information, date of stroke, time since stroke, ethnicity, brief post-stroke medical history. Data that will be recorded from human subjects will include rating-scale assessments of upper extremity motor ability, kinematic motion analysis of upper extremity movement, measurements of upper extremity strength, and upper extremity electromyography. Identifiable information will be stored in password-protected files on a secure MUSC network (MUSC patients) or on the VA-network (VA patients). All data will be coded with a unique study identifier. The only people having access to this identifiable information will be [name] and her research study staff (named on this protocol). No other person will have access to PHI for study participants. All data will be de-identified with all personal identifiers removed for data analysis. That is, the PHI will be stripped of its identifiers for data analysis. Data analysis will incorporate only aggregate data that does not contain any participant-specific identifiers. There will be no way to link the data being analyzed back to the individual. Hard copy data will be coded by unique study identifier and stored in a locked file cabinet which is located along the east wall of the secured office of the principal investigator which is located in room #307 of the College of Health Professions Research Building at [name]. This space is designated as a VA research space in a VA approved memorandum of understanding. Once the study is completed data (described below) will be de-identified. Potential participants will be identified through recruiting mechanisms described above associated with the MUSC Stroke Center and VA PM&R service. The PI and/or study coordinator for the present study will provide the MUSC Stroke Center and VA PM&R service with inclusion/exclusion criteria. Personnel associated with either of these places will then provide our contact information to participants. Participants will then initiate contact with either the PI or Study Coordinator of the present study. If potential participants meet inclusion criteria they will be asked by the study coordinator if they would like to participate in the current study. If they do wish to participate, they will be scheduled for a time to obtain written informed consent to participate in the study.

c. Potential Risks

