1. Experienced an ischemic stroke at least 3 months prior
2. Passive range of motion in affected shoulder, elbow, and wrist within functional limits
3. 20-80 years of age

Exclusion criteria:

1. Pain in the affected upper extremity that would interfere with movement
2. Unable to understand 3-step directions
3. Unable to attend the study-related treatment or evaluation sessions
4. Orthopedic condition in back, UE, or impaired corrected vision that would alter kinematics of reaching.

1. Date of stroke_____
2. Medical records and MRI or CT available for review before participation yes no
3. Adult age 20 – 80? Current age_____
4. Gender: Male Female
5. Affected side: left right
6. Do you have passive ROM
 - a. Shoulder yes no
Motions_____
Limitations_____
Pain with PROM yes no scale: 1 2 3 4 5 6 7 8 9 10
Does your pain interfere with movement: yes no
 - b. Elbow yes no
Motions_____
Limitations_____
Pain with PROM yes no scale: 1 2 3 4 5 6 7 8 9 10
Does your pain interfere with movement: yes no
 - c. Wrist yes no
Motions_____
Limitations_____
Pain with PROM yes no scale: 1 2 3 4 5 6 7 8 9 10
Does your pain interfere with movement: yes no

7. Able to understand 3-step directions: yes no

Ex: 1. Place your right hand on the table.
 2. Tap your index (pointer) finger 3 times on the table.
 3. Make a fist with your right hand.

8. Total study time will be 8 weeks. All participants, in all groups will engage in 4 evaluations, 9 rehabilitation sessions and 1 follow-up session which will be 30 days after the last rehabilitation therapy session. The first session will take approximately 3-4 hours and all other sessions will take approximately 3 hours.

Are you willing and available to participate in all sessions and follow-up yes no

9. Do you have orthopedic back conditions that prevent you from:

a. Sitting up for prolonged periods without trunk support yes no
 b. Sitting on a chair/stool without back support yes no

c. Do you have pain during or after sitting unsupported on a chair yes no

Pain scale: 1 2 3 4 5 6 7 8 9 10

Does your pain interfere with movement yes no

d. Do you wear splints, slings, or other supportive devices on your hands or wrist yes no

e. Do you wear an eye patch yes no

f. Do you have impaired corrected vision that would alter your ability to reach or grasp objects? yes no

Notes: _____

Questionnaire was conducted:	Phone	With Individual	Caregiver	Both
	In person	With individual	Caregiver	Both

 Recruiter

 Date of Questionnaire

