**Medical University of South Carolina
Statistical Analysis Plan**

PI Name: [name], OTR/L

Study Title: Patient-Targeted Upper Extremity Rehabilitation After Stroke

Identifiers: NCT01819506 **Unique Protocol ID:** N0799-R

Version 4.0

Date: 08/01/2016

Statistical Analysis Plan

Aim 1: To test the effect of patient-specific targeted practice. Rationale: We hypothesize that task practice at the just-right challenge of difficulty will maximize post-stroke motor skill reacquisition. We expect that “targeted practice”, will increase UE motor ability because the difficulty of task goals will be matched and systematically progressed according to patients’ initial and evolving levels of ability. The Rasch UE motor ability measurement framework defines levels of UE motor ability by describing UE movement tasks (FMA-UE items) which patients in each level can easily perform, cannot perform (too hard), and are well-matched to ability level. This information is the basis for designing and progressing task-practice sessions to specifically target patient-specific movement abilities.

Approach: Dependent Variable: The dependent variable will be the Rasch FMA-UE person measure. Independent Variables: The independent variables are Group and Time. The between subjects factor “Treatment” has 2 levels (Targeted vs. Non-Targeted therapy) with 3 impairment levels nested within each level (mild, moderate, severe). The within subjects factor “Time” has 3 levels; Pre, Mid, Post. Data Analysis: A two-way mixed model ANOVA will be used to assess the main effect of Treatment. Significance for all comparisons will be alpha = 0.05. Covariate: intensity of training (averaged number of repetitions per session).

Missing Data: Since each patient will be observed over a 3-week period it is possible that the patient will miss a visit and/or drop out. If a patient misses a testing session, the session will be rescheduled to the next visit. If the patient drops out an intent-to-treat analysis will be applied and the missing data will be treated as missing at random (MAR). If missing occurs, multiple imputation methods will be used for data analysis (PROC MI and PROC MIANALYZE, in SAS version 9.3). This process will be overseen by the biostatistician [name].

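### Aim 1 does not prespecify adjustment for time since stroke, which is recorded, has no upper limit at entry and is absent from the strata; the precision at stake is unknown, and adding it costs one degree of freedom per term

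*Protocol*

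**What the plan says.** **Collection.** Protocol section E, Sources of Materials, lists among the items obtained from participants "date of stroke, time since stroke".

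**Entry window.** Section D (Inclusion criteria) requires that the patient "experienced ischemic stroke at least 3 mo. prior". Section E has "Experienced a stroke at least 3 months prior that has resulted in unilateral hemiparesis", and the recruitment questionnaire in Appendix J has "Experienced an ischemic stroke at least 3 months prior". None gives an upper limit.

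**Likely spread.** Section C, 3b, describes the group's earlier cross-sectional cohort as "an average of 7 years post first time ischemic stroke". Section D (Recruitment) draws on a stroke center that sees over 50 new patients a month and on veterans treated in 2007-2010; the protocol is dated August 2016.

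**Allocation.** Section D (Study Design) randomises within the three impairment levels. No other stratification factor is named.

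**Aim 1 models.** Section D (Specific to Aim 1) has treatment group as the only independent variable, compared within each impairment level on percent change. The SAP, Aim 1, states "The independent variables are Group and Time". It nests impairment level within treatment and analyses the person measure at Pre, Mid and Post. Its one covariate is average repetitions per session, which is measured after randomisation.

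**The concern.** Patients three months after stroke and patients many years after stroke may enter the same impairment level. If the Rasch FMA-UE or its change varies with time since stroke, that variation is counted as noise in Aim 1, although a pre-treatment measurement that could absorb it is already on file. Each level has only about 18 patients per group, and allocation does not balance time since stroke by design. What is at stake is precision. It matters most for the protocol's per-level tests, where the corrected alpha already takes power below the planned 90%.

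**Working it through.** **Inputs from the protocol (section D, sample size and Specific to Aim 1).** Pilot post-training means (SD) are 2.30 (1.00) and 1.42 (0.45) logits. The plan uses d = 1.13, two-sided alpha 0.05, 90% power and 18 per group in 6 groups. The protocol's corrected alpha is 0.05/3 = 0.0167, which it prints as 0.02. The SAP's alpha is 0.05.

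**Input not in the documents.** R², the share of residual outcome variance within impairment level explained by time since stroke, is assumed at 0.05, 0.10 and 0.20 (correlations of about 0.22, 0.32 and 0.45). Zero is also possible.

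**Step 1: reproduce the plan's figure.** Pooled SD = √((1.00² + 0.45²)/2) = √0.601 = 0.775. Then d = 0.88/0.775 = 1.135, against 1.13 stated. The noncentral t gives 17.5 per group for 90% power at alpha 0.05, rounded up to 18, and 6 × 18 = 108. The figure reproduces, and it assumes no covariate.

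**Step 2: unadjusted power at 18 per group.** The noncentrality is 1.13 × √(18/2) = 3.39 on 34 degrees of freedom. Power is 0.909 at alpha 0.05 and 0.803 at alpha 0.05/3.

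**Step 3: adjusted power.** The residual SD is multiplied by √(1 − R²), so d becomes 1.13/√(1 − R²). One degree of freedom goes to the covariate, leaving 33.

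| Assumed R² | Adjusted d | Power, alpha 0.05/3 | Power, alpha 0.05 | Equivalent extra patients, 1/(1 − R²) − 1 |
|---|---|---|---|---|
| Unadjusted | 1.130 | 0.803 | 0.909 | – |
| 0 | 1.130 | 0.802 | 0.908 | 0% |
| 0.05 | 1.159 | 0.82 | 0.92 | 5% |
| 0.10 | 1.191 | 0.85 | 0.93 | 11% |
| 0.20 | 1.263 | 0.89 | 0.96 | 25% |

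**Step 4: the SAP's pooled test.** With 3 × 18 = 54 per arm, d = 1.13 and alpha 0.05, the noncentrality is 1.13 × √(54/2) = 5.87 and power is already about 1.00. At the plan's own effect size the adjustment adds nothing visible there. It would matter only for a smaller effect, and the documents give none.

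**Step 5: where the covariate acts in the SAP model.** Time since stroke at randomisation is constant over Pre, Mid and Post. Entered as a main effect, it can reduce only the between-patient variance in average level. Variation in gain that depends on it stays in the within-patient error unless its interaction with Time is also in the model.

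**The case against.** **The association is not shown.** A reader might infer that a known source of outcome variation has been left out. The documents do not support that. The 7-year figure is a mean from a separate cross-sectional study; it gives no spread and no relation to gain. Two titles in the reference list mention time since onset or a limited post-stroke window, which makes the variable plausible but supplies no effect for this population. The baseline factor that section D does tie to response is motor deficit, and impairment level already carries much of it in the strata and in the SAP model. This objection stands, and it is why the gain is stated only under assumptions.

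**The power figures do not describe either planned outcome exactly.** The plan's d comes from post-training levels. The protocol analyses percent change, and the SAP analyses the person measure over three visits. This also stands: the table shows scale on the plan's own d and does not predict power for either analysis.

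**Chance imbalance is not a further problem.** A reader might infer that an uneven split of early patients biases a level's estimate on top of the lost precision. Suppose 20% are early and gain an extra 0.5 to 1.0 logit (both assumed). The difference in share has SD √(2 × 0.2 × 0.8/18) = 0.133, which moves the estimate by an SD of 0.07 to 0.13 logits. The extra variance is 0.2 × 0.8 × (0.5² to 1.0²) = 0.04 to 0.16, or 7% to 27% of 0.601. That is the R² scenario restated. It is ordinary sampling error, set against a standard error of √(2 × 0.601/18) = 0.26 logits, and is not a systematic bias.

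**Other recorded variables could be argued for in the same way.** This is partly true. Time since stroke has a stronger case than most because its entry range is open above and the SAP already accepts a covariate, though one measured after randomisation.

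**Conclusion.** The point holds as a matter of precision. Time since stroke is recorded, unbounded above 3 months, and in neither the strata nor either Aim 1 model. At the plan's d with 18 per group, adjustment would add about 2 to 9 points of power at alpha 0.05/3, and about 1 to 5 points at alpha 0.05, if R² lies between 0.05 and 0.20. If there is no relation it would cost about 0.1 point. R² is assumed throughout, so the true benefit may be nil. The documents do not support reading the omission as a bias or as an error in the sample size: randomisation protects the comparison, and the 18 per group was derived without covariates. The case for acting is that the possible loss is trivial, and that choosing the covariate after outcomes are seen would invite selective adjustment.

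**What to change.** In the protocol's per-level Aim 1 comparison of change, prespecify log(months since stroke at randomisation) as a baseline covariate. In the SAP's mixed model, include the same covariate together with its interaction with Time, so that it can reduce error in gain as well as in level. State the log form in advance, because the range is open above and probably skewed.

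The cost is a sentence in each document, one degree of freedom in the per-level comparison, and a few more in the SAP model for the interaction with the three-level Time factor. No new data are needed.
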